10.2.2 Demographic and baseline parameters

Demographic and baseline parameters including sex, age, race, ethnicity, height and weight, medical history, smoking history, details of initial diagnosis and treatment history will be summarized overall and by group. All continuous variables will be summarized by descriptive statistics. All discrete variables will be summarized by frequencies and percentages.

10.3 Interim analysis

A single formal interim comparative analysis of the epigenetic patterns in blood-derived DNA from control subjects with no malignant disease and subjects at risk for developing the investigated hematological malignancies and the patterns obtained for all malignant and premalignant hematological conditions will be conducted after approximately 24 months from the beginning of the study and will include:

Comparative analysis for 250 newly diagnosed NHL samples with HemaChip

Comparative analysis for 250 newly diagnosed MM samples with HemaChip

Comparative analysis for 100 samples of the following conditions: SMM, MGUS, HL, AML, MDS, control subjects with no malignant disease and subjects at risk for developing the investigated hematological malignancies.

10.4 Sample size and power calculation

The sample size of each stage of the clinical study will be determined in accordance with technology development requirements. Hence, three designs should be taken into account: Discovery stage performed with high density discovery chip, and validation and screening stages performed with targeted HemaChip. All the calculations below have been made with optimistic assumptions that we will be able to prepare such sensitive chips that classify the studied hematological malignancies types with expected target sensitivity of above 95%. Moreover, the minimal sensitivity 80% was set as a lower bound for all statistics to get a scale for the further Sample Size calculation. Importantly, based on incidences of particular diseases the calculated Sample Size will include significant proportions of all diseases of interest.

Discovery stage:

The method Proportion sample size determination for binomial distribution (arcsine transformation, significance level = 0.05, test power = 0.8) was used to analyze the required sample size. Based on previous experiments, we propose two estimates – expected target sensitivity, and minimum acceptable sensitivity. Estimate of the expected target sensitivity of the discovery chip was set to 95%. This estimate is needed to set the minimum acceptable limits for establishing statistical tests and represents the best expected result that could theoretically be achieved with the current state of technology and knowledge. The estimate of the minimum acceptable sensitivity of the discovery chip was set to 89%. The value is based on reported literature and the fact that this phase is conducted on diagnosed patients with active disease.

Expected Sensitivity	Sample Size
0.84	569
0.85	356
0.86	241
0.87	173
0.88	128
0.89	99
0.90	77
0.91	62
0.92	50
0.93	41
0.94	34
0.95	30
0.96	23
0.97	19

[figure not shown]

Figure 1. Required sample size for discovery microarray, analyzed by Proportion sample size determination for binomial distribution (arcsine transformation, significance level = 0.05, test power = 0.8).

As evident from Figure 1, the larger the deviation of the observed sensitivity from the 80% value, the smaller the sampling size required to prove that the actual sensitivity of the tested discovery array is statistically significantly higher than 80%. In case of the optimistic estimate, it is expected the sensitivity of the chip designed for the disease detection to be 95%, which corresponds to a minimum sample size of 30 subjects for each disease subtype. In the context of the mentioned numbers, and the confidence level of 95%, the confidence interval will be 0.817, and 0.999. In case of the minimum acceptable estimate, the sensitivity of the discovery array is set to be 89%, which corresponds to a sample size range of about 99 subjects per disease. In the context of the mentioned numbers, and the confidence level 95%, the confidence interval will be 0.810, and 0.943.

Since the real sensitivity of the discovery is unknown and based on experience with 60,000 pixel arrays, we have decided to start with a set of 30 subjects and use the data for more precise and evidence based power calculation. The selection of the biomarker panel may be performed even under this uncertainty by including also more variable markers in the HemaChip panel and further tune the array once sufficient data has been accumulated.

Validation stage:

The large discovery chip serves as a matrix for selecting significant markers and as an experimental platform for the final targeted HemaChip design with a reduced number of spots/markers. Here, the same statistics need to be performed to prove that the HemaChip will work with a high statistical accuracy. Since there has been a reduction in markers, we will assume that the sensitivity of the chip will be at a lower level, yet still above the minimum threshold of 80%. With the same test setup (arcsine transformation, significance level = 0.05, test power = 0.8) and the expected specificity of 85% (lower bound), approximately 356 subjects (Sample size) will be needed to verify the results. In the context of the mentioned numbers, and the confidence level 95%, the confidence interval will be 0.810, 0.887 (Figure 12).

The research program is designed to test diagnosed ~250 subjects of MM and NHL, and 100 subjects of the remaining conditions in the validation stage. If the selection of biomarkers was sufficiently good, the expected sensitivity of the HemaChip will not dramatically decline relative to

the discovery array and this number of tests should suffice. Accumulation of additional data is expected in the next phases of the project in order to accurately tune the statistical analysis according to the data.

[figure not shown]

Figure 2. Required sample size for HemaChip, analyzed by Proportion sample size determination for binomial distribution (arcsine transformation, significance level = 0.05, test power = 0.8).

Stage 3: Screening at-risk cohorts

When calculating the sample size for the screening stage, the incidences of individual types of hematological malignancies were considered. The assumption is that the individual types will occur in the same proportion also in the risk cohorts of patients. We also consider the minimum number of samples with respect to the HemaChip and its expected sensitivity (as detailed in stage 2), and the known fact that the incidence of the hematological malignancies is about five percent in the risk cohort. Then, the sample population was determined to be approximately 7120. Such a screen is beyond the scope of this project but given that the tests performed side by side with standard diagnosis, the incidence rate is sufficient to derive initial performance metrics based on several hundred tests. Positive results will allow performing a large scale clinical study needed for screening purposes.

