10 STATISTICAL CONSIDERATIONS

10.1 Study design

Controlled study - This study aims to identify methylation patterns indicating the presence of cancer. Comparison to control participants with no malignant diseases is essential for identifying tumor-specific methylation patterns.

Open study - The current study is an open study where all participants are divided into known groups. For the first stage of the study, the group identification is essential for discovery of biomarkers for each disease type. Discovery stage will be based on empirical comparison between controls and patients diagnosed with various hematological cancers. Therefore, group identification is required for validation, comparison with state-of-the-art diagnosis and disease status.

The current study contains only one type of intervention and therefore randomized/crossover or parallel groups are inapplicable.

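### Section 10.4 does not secure the independence that its binomial tests of sensitivity against 80% assume, in discovery or in validation.

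*Protocol*

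**What the plan says.** **Stage 1.** Section 10.4 states that "the minimal sensitivity 80% was set as a lower bound for all statistics" and uses a binomial method ("arcsine transformation, significance level = 0.05, test power = 0.8"). Its purpose is "to prove that the actual sensitivity of the tested discovery array is statistically significantly higher than 80" per cent. At an expected sensitivity of 95% the protocol gives a size "which corresponds to a minimum sample size of 30 subjects for each disease subtype". Section 4.1 and Table 1 recruit at least that number per group. The same part of 10.4 describes the discovery chip as the source from which significant markers are chosen. Primary endpoint 1 in section 3 combines defining the markers with determining sensitivity and specificity.

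**HemaChip.** At the end of the discovery text, 10.4 accepts choosing the panel under uncertainty, by including more variable markers, and then plans to "further tune the array once sufficient data has been accumulated". The validation text applies the same test to the HemaChip. It ends by expecting more data in later phases "in order to accurately tune the statistical analysis according to the data". Section 8 places both the development and the use of the HemaChip in years 2-3. No point is named at which the version under validation is fixed.

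**Labels.** Section 10.1 describes an open study with known groups and adds: "Therefore, group identification is required for validation, comparison with state-of-the-art diagnosis and disease status".

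**The concern.** The sample sizes and intervals in 10.4 hold for one fixed classifier applied to subjects who played no part in building it. That condition can fail in two ways.

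- **Discovery.** If sensitivity is estimated in the 30 subjects per group who select markers from a very large array, the estimate mostly reflects selection. Section 10.4 also intends to use these data for a better power calculation, so an inflated figure would carry into later sizing.
- **Validation.** If the chip or its analysis is adjusted on labelled samples that then count towards the test against 80%, the reported sensitivity is too high and the error rate exceeds its nominal level. Primary objective 2, validation of the HemaChip, would rest on data that shaped the test. Section 1.2 says the results may support marketing approvals.

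**Working it through.** **1. Reproduce the protocol's sample sizes.** Inputs from 10.4: null sensitivity 0.80, significance level 0.05, power 0.80, arcsine method. One-sample formula:

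`n = [(z_alpha + z_beta) / h]^2`, with `h = 2*asin(sqrt(p1)) - 2*asin(sqrt(0.80))`

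One-sided, z_alpha + z_beta = 1.645 + 0.842, and 2*asin(sqrt(0.80)) = 2.2143.

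- p1 = 0.89: h = 0.2512, n = 98.01, rounded up to 99 (stated 99).
- p1 = 0.85: h = 0.1319, n = 355.4, rounded up to 356 (stated 356).
- p1 = 0.95: h = 0.4763, n = 27.3, rounded up to 28 (stated 30).

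Two-sided 0.05 would give 125, 452 and 35, so the table is one-sided, although the text does not say so. The quoted intervals are exact binomial ones: 27/28 gives 0.817-0.999, 88/99 gives 0.810-0.943 and 303/356 gives 0.810-0.886 (stated 0.887). The arithmetic therefore assumes a fixed rule and independent subjects.

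**2. Discovery: what if the selecting subjects are also the test subjects?** Simulation with no true signal: 60,000 independent features (the array size that 10.4 mentions), 30 cases against 30 controls, the top 20, 100 or 500 markers kept, a linear classifier, 40 runs per setting. Sensitivity in the selecting subjects was 99%, 100% and 100%. In new subjects it was 49 to 50%. The test against 80% was passed in every run.

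**3. Validation: what if tuning uses the validation cases?** Set true sensitivity at 0.80. The exact one-sided 5% rule is at least 87/100 (actual error 0.047) or at least 211/250 (0.045). Let K tuned variants be tried on the same cases and the best one tested. K and the latent correlation between variants are assumptions; the protocol gives neither. False claims of more than 80%:

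| K | n=100, correlation 0 / 0.5 / 0.8 | n=250, correlation 0 / 0.5 / 0.8 |
|---|---|---|
| 1 | 4.8 / 4.8 / 4.6% | 4.6 / 4.6 / 4.7% |
| 3 | 14.0 / 12.0 / 10.9% | 13.1 / 12.2 / 10.2% |
| 5 | 21.9 / 18.1 / 15.5% | 20.8 / 17.4 / 14.1% |
| 10 | 38.4 / 30.0 / 22.0% | 37.5 / 29.4 / 21.7% |

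Check for n=100 at correlation 0: 1 - 0.9531^K gives 13.4%, 21.4% and 38.1%, in line with the simulation. At K = 5 the mean apparent sensitivity is 0.83-0.85 (n=100) and 0.82-0.83 (n=250).

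**4. Which data could be used for tuning?** Stage 1 runs on a commercial array, so HemaChip data exist only from Stage 2 on. Stage 3 has up to 900 subjects; at the 5% incidence that 10.4 assumes, that is 900 x 0.05 = 45 cases over all malignancies.

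**5. Power if part of Stage 2 is set aside for tuning.** Power = Phi(sqrt(n) x h - 1.645). At 0.89 (h = 0.2512):

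- n = 100: 81%; n = 80: 73%; n = 50: 55%.
- n = 250: 99%; n = 125: 88%.

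At 0.85, the protocol's lower expectation for the HemaChip, the full Stage 2 gives only 67% (n=250) and 37% (n=100).

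**The case against.** Section 10.4 is a sizing section and specifies no estimator. The 80% figure is introduced there to set a scale for sample size, and nothing says that Stage 1 sensitivity will be computed in the selecting subjects without correction. Cross-validation, a lock date and the handling of labels are commonly left to the statistical analysis plan, which section 10.6 names. This stands as far as missing detail goes. It does not cover the text that is there: a stated proof against 80% sized on the marker-selection subjects, and sentences that foresee tuning. A later lock would have to override those sentences.

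A reader might infer that the protocol plans to tune on the Stage 2 validation samples. It does not say so. The array-tuning sentence sits in the discovery text and can mean more discovery data, since 30 is a minimum and section 5.5 allows more samples. The analysis-tuning sentence refers to later phases and may mean refining the power calculation. What remains is that no wording excludes Stage 2.

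A reader might also infer that Stage 1 reuse contaminates the validation. Table 1 counts Stage 2 subjects separately, so only tuning could do that.

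Finally, section 10.1 might be read as giving diagnoses to those who make the chip calls. Scoring against a reference diagnosis needs the labels in any case, Table 2 assigns barcodes, and section 10.2.1 says samples are anonymised. That sentence is not an error.

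**Conclusion.** The concern holds as a lack of security, not as proof that either sensitivity claim is dependent. For Stage 1, 30 subjects per group and the interval 0.817-0.999 carry no information about true sensitivity if the estimate is made in the selecting subjects. The noise simulation is the extreme case and shows that such an estimate cannot tell signal from none. For Stage 2, tuning on counted cases would raise a 5% error to about 10-14%, 14-22% or 22-38% with three, five or ten variants. This rests on the assumed number of variants, a latent correlation of 0 to 0.8, and a one-sided test inferred from the sample-size table. The protocol's sample sizes are essentially right as arithmetic; they presuppose an independence that the plan does not fix. This should be fixed. Confidence is moderate, because the validation half depends on how the tuning sentences are read.

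**What to change.** In section 10.4:

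1. Replace the Stage 1 proof against 80% with an estimate from cross-validation in which marker selection is repeated inside each fold, labelled as planning information only.
2. Replace both tuning sentences with a statement that marker panel, chip layout, algorithm and cut-offs are locked before the first Stage 2 sample counted for validation is read. Any later tuned version is either reported as exploratory or tested only in samples not used for tuning.

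Making calls under the existing barcode and joining diagnoses only afterwards is a sensible safeguard to add.

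The cost is wording and some analysis work, with no extra subjects. Locking before Stage 2 is preferable to taking a tuning subset from Stage 2. At 0.89, using 20 of 100 cases lowers power from 81% to 73%, and using half lowers it to 55%; half of 250 lowers it from 99% to 88%. Stage 2 is already below the 356 that 10.4 requires at 0.85. The change has to be made before Stage 2 chips are read, because a validation set used for tuning cannot be restored.

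### The validation-stage numbers (250 or 100 per condition) fall short of the 356 that section 10.4 derives, and the sensitivity and power they rely on are not stated

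*Protocol*

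**What the plan says.** All of this is in the validation-stage part of Protocol section 10.4 unless another place is given.

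- **Assumption for the HemaChip.** Because the marker set is reduced, "we will assume that the sensitivity of the chip will be at a lower level, yet still above the minimum threshold of 80" per cent.
- **Test.** "With the same test setup (arcsine transformation, significance level = 0.05, test power = 0.8"), with the planning value printed as "the expected specificity of 85% (lower bound"). The comparison value comes from the opening of section 10.4: "the minimal sensitivity 80% was set as a lower bound for all statistics".
- **Result.** "approximately 356 subjects (Sample size) will be needed to verify the results", with a 95% confidence interval of 0.810 to 0.887.
- **Numbers planned.** "The research program is designed to test diagnosed ~250 subjects of MM and NHL, and 100 subjects of the remaining conditions". Section 4.2 and Table 1 in section 5.1 give the same numbers as minimums. One figure of 250 covers DLBCL, FL and MZL together. MGUS, SMM, HL, AML and MDS have 100 each.
- **Bridge between the two.** If biomarker selection was good enough, HemaChip sensitivity is expected to stay fairly close to that of "the discovery array and this number of tests should suffice". No sensitivity and no power are given for 250 or 100.

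**The concern.** The section derives a required number from a deliberately cautious sensitivity. It then adopts smaller numbers on the strength of a more favourable sensitivity that it never states. The reader cannot tell what the planned groups can show.

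Validation of the HemaChip is primary objective 2 (section 2), and assay sensitivity at each stage is a primary endpoint (section 3). If the HemaChip performs at the planning value, a result that does not exceed 80% would be likely in the smaller groups through sample size alone, and it could be misread as a failure of the assay. Section 1.2 says that the results may be used for marketing approvals, so the planned precision should be on record.

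**Working it through.** **Inputs (all from section 10.4).** Bound p0 = 0.80; planning value p1 = 0.85; arcsine method; significance level 0.05; power 0.80. Sidedness is not stated. The discovery-stage text describes showing that "the actual sensitivity of the tested discovery array is statistically significantly higher than 80" per cent, which points to a one-sided test. No allowance for dropout is stated, and none is applied here.

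**Step 1: reproduce 356.**

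h = 2·asin(√0.85) − 2·asin(√0.80) = 0.1319

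n = ((z(0.95) + z(0.80)) / h)² = ((1.645 + 0.842) / 0.1319)² = 355.4, rounded up to 356.

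This matches. A two-sided test gives 451.2, so 452, which does not. The one-sided formula also gives every row of the section 10.4 table to within 2 subjects; the largest gap is the 0.95 row, where it gives 27.3, so 28, against 30 printed. The protocol's calculation is therefore one-sided.

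**Step 2: power at the planned numbers, true sensitivity 85%.**

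Power = Φ(h·√n − 1.645)

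| n | One-sided arcsine | Exact binomial, one-sided 0.05 | Two-sided arcsine |
|---|---|---|---|
| 356 | 80.1% | 77.8% | 70.1% |
| 250 | 67.0% | 64.5% | 55.0% |
| 100 | 37.2% | 34.7% | 26.1% |

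The exact test needs at least 211 of 250 or 87 of 100 subjects classified correctly. On the arcsine figures, the chance of missing significance at 85% is 1 − 0.670 = 33% with 250 subjects and 1 − 0.372 = 63% with 100.

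**Step 3: expected 95% confidence intervals at 85% (exact method).**

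- n=250: about 0.80 to 0.89, so the lower limit sits at the bound.
- n=100: about 0.765 to 0.914, which includes 80%.
- n=356: the protocol prints 0.810 to 0.887, which excludes 80%.

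**Step 4: sensitivity at which the planned numbers give 80% power.** Solving the Step 2 formula for p1 gives 0.859 at n=250 and 0.889 at n=100. The protocol's table agrees: 241 subjects at 0.86 and 99 at 0.89. At a true sensitivity of 89%, power is 99.0% with 250 subjects and 80.7% with 100 (exact 79.2%).

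**Step 5: compare with the stated assumption.** Section 10.4 sets 89% as the minimum acceptable sensitivity of the discovery chip. The 100-subject groups therefore reach 80% power only if the HemaChip performs at or above that value. The same section assumes that the HemaChip is less sensitive than the discovery chip and uses 85% as its lower bound.

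**The case against.** A reader might infer that the protocol claims 80% power for 250 and 100 subjects and that the claim is false. The text does not support that. It attaches 80% power only to 356 subjects, and it prints 356 and the smaller numbers close together. Its reassurance is conditional, and 85% is labelled a lower bound rather than the expected value. A fall from the 95% target to about 89% could fairly be called both lower and not dramatic, and at 89% the planned numbers do give about 80% power or more. All of this stands. What it leaves is a condition without a figure, replacing a calculation that had one.

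The per-condition reading of 356 can also be challenged. The number carries no such label, and stage 3 appears to use it across malignancies, since 7120 × 0.05 = 356. On a pooled reading, the stage 2 minimum of 1000 subjects exceeds it easily. This is a real ambiguity. The per-condition reading is still the stronger one: the validation stage uses the same test setup as the discovery stage, whose numbers are per disease, and 356 is followed directly by 250 and 100. If 356 were a pooled total, no conditional reassurance would be needed.

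Finally, the planned numbers are minimums, section 5.5 allows more samples in a subgroup, section 12.5 allows extension, and section 10.4 foresees a better power calculation once discovery data exist. These provisions could lead to adequate numbers. They do not correct the present statement.

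**Conclusion.** The point holds as a gap between the protocol's own requirement and its planned numbers. The arithmetic behind 356 is correct. At the protocol's own 85%, power is about 67% for MM and for pooled NHL, and about 37% for each of MGUS, SMM, HL, AML and MDS. For 80% power the planned numbers need a true sensitivity of about 0.86 and 0.89 respectively, and the protocol does not say that it relies on those values.

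The figures rest on three readings: the test is one-sided (the only version that reproduces 356), 356 is per condition (a strong inference, not stated text), and the printed 85% specificity means sensitivity, as the preceding sentence and the table indicate. Under a two-sided test, power would be lower still.

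The 250 NHL subjects pool three subtypes, so precision for DLBCL, FL or MZL alone will be lower than for the pooled group. The protocol gives no split for stage 2, so no subtype power can be calculated. Nor do the documents show that the 100-subject groups are useless for testing: they are adequately sized if sensitivity is about 89%.

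**What to change.** Amend the validation-stage text of section 10.4; the planned numbers can stay.

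- Replace the statement that the number of tests is enough with the operating characteristics. For n=250: power 67% at 85%, 80% power from a true sensitivity of about 0.86, expected 95% interval at 85% of about 0.80 to 0.89. For n=100: power 37% at 85%, 80% power from about 0.89, expected interval about 0.765 to 0.914.
- State that the test is one-sided and that 356 is a per-condition number.
- Correct the 85% from specificity to sensitivity.
- Note that the 250 NHL subjects combine DLBCL, FL and MZL, so precision per subtype is lower.

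The cost is a wording change with no extra patients. The drawback is that the stated operating characteristics look less favourable than the present text suggests.

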1 BACKGROUND AND STUDY RATIONAL

Approximately 10% of cancer cases in Europe account for hematological malignancies, including leukemias, lymphomas and myelomas. In 2020, 293,775 people in Europe were diagnosed with hematological malignancies, and 148,394 people died¹. Despite advances in drug development and emerging targeted therapies, effective and early diagnosis combined with population screening remains the most powerful tool for fighting cancer. In general, there is an urgent need to have minimally-invasive methods to screen and detect hematological malignancies. For cancer management, these tests are needed to quantify pre-treatment and residual tumor burden to provide useful prognostic information before treatment, to assess molecular response at interim time points and minimal residual disease (MRD) at the end of treatment, and to identify tumor-specific abnormalities when possible.

Bone marrow biopsy, considered the gold standard of multiple myeloma (MM) diagnosis and indicated conditions of other hematological malignancies, provides only a snapshot of the disease at the moment taken and is an invasive method, coming with its risks. However, patients diagnosed with MM and other hematological malignancies require continuous painful follow-up biopsies to monitor the condition, this may indeed lead to avoidance of follow-up visits by patients and subjects at risk of being unwilling to get regular screening. For non-Hodgkin's lymphomas (NHL) and Hodgkin's lymphomas (HL), lymph node biopsy is the gold standard for their diagnosis. Newly developed minimally-invasive diagnostic tools based on liquid biopsy may complement and possibly eventually overcome conventional biopsies. Liquid biopsy can provide real-time feedback on patient condition based on systematic and routine measurements of critical biomarkers - a characteristic that is objectively measured and evaluated as an indicator of normal biological processes or pathogenic processes. Despite extensive progress, research and development are still needed before implementation of liquid biopsy-based tests as the standard of care.

Accumulating evidence shows that epigenetic changes provide unique signatures indicating disease type and stage². These modifications will be detected in genomic DNA extracted from peripheral blood cells, as well as from cell-free and exosomal DNA arising mostly from dying cells, cancer or healthy.

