4.4 Clinical follow-up

Subjects that serve as controls, subjects at risk (from the Third stage) and a subset of patients from the First and Second stage are expected to donate blood a single time. Following this donation, their participation will end.

For a subset of patients from the Second stage it is expected, after signing the informed consent forms, that serial samplings will be performed during the disease follow-up according to the standard clinical practice and/or recommended schedule and disease assessment plan (see Table 3).

All follow-up patients will be followed for a period of up to 36 months.

For this clinical trial, demographic and baseline parameters including sex, age, race, height and weight, medical history, smoking history and status, details of initial diagnosis and treatment history concomitant medications as well as adverse events (AEs) of special interest (see section 9.1), (serious) AEs related to study procedure, treatment for the disease, disease response and survival status will be collected (as applicable).

Subjects who complete the main study, may be followed up for their disease status, anti-cancer

treatments, concomitant medications, new primary malignancy and survival, following statistical review of the study results. Serial blood samplings will be performed during the long-term follow-up according to the standard clinical practice and/or recommended schedule and disease assessment plan (see Table 3).

A detailed plan for long-term follow-up beyond the main study will be provided as an amendment to this protocol.

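### Section 10.4 supports Stage 3 with an uncited 5% incidence of malignancy, but a single blood draw needs the prevalence of undiagnosed disease, so its claim of enough cases is unsupported for malignancy

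*Protocol*

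**What the plan says.** Section 10.4 reaches its Stage 3 reference figure in two steps. The validation stage tests against a fixed minimum: "the minimal sensitivity 80% was set as a lower bound for all statistics". The method is carried over from discovery: "With the same test setup (arcsine transformation, significance level = 0.05, test power = 0.8". For an expected value of 85%, the text gives "the expected specificity of 85% (lower bound), approximately 356 subjects (Sample size) will be needed to verify the results". The text says specificity, but 356 is the row for an expected sensitivity of 0.85 in that section's table.

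The Stage 3 paragraph then brings in "the known fact that the incidence of the hematological malignancies is about five percent in the risk cohort" and concludes that "the sample population was determined to be approximately 7120". No source or time unit is given for the five percent. On case mix it adds: "The assumption is that the individual types will occur in the same proportion also in the risk cohorts of patients".

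The same paragraph says that a screen of this size will not be done in this project. It nevertheless asserts that the rate is high enough for first performance estimates from several hundred tests. Sections 4.3 and 5.1 fix Stage 3 at up to 900 subjects: 400 elderly and 500 first-degree relatives. Under Section 4.4, controls and at-risk subjects "are expected to donate blood a single time. Following this donation, their participation will end". The protocol's only population count of these diseases is in Section 1: "In 2020, 293,775 people in Europe were diagnosed with hematological malignancies, and 148,394 people died".

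**The concern.** The five percent does two jobs. It turns 356 cases into 7,120 subjects, and it supports the statement that the Stage 3 actually planned will contain enough cases to be informative. It is called an incidence, which counts new cases over time. Stage 3 has no follow-up time, so a single draw can find only disease that is already present.

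Five percent also looks far too high for malignancy beside the European count in Section 1. If it is, Stage 3 will contain almost no malignancies. Primary objective 4, which asks for sensitivity as well as specificity in the at-risk populations, would then have almost no data on sensitivity for malignancy.

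**Working it through.** **1. Reproduce the plan's figures.** The inputs are null 0.80, expected 0.85, alpha 0.05 and power 0.80, all from Section 10.4. The one-sample arcsine formula is n = [(z for alpha + z for power) / (2·asin√0.85 − 2·asin√0.80)]².
- One-sided alpha: (1.645 + 0.842)² / 0.1319² = 355.4, so 356. This matches.
- Two-sided alpha: 451.2, so 452. This does not match.
- 356 / 0.05 = 7,120. This matches exactly.

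The arithmetic is therefore sound, and the question is only about the 5% input.

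**2. Read 5% as annual malignancy incidence.** With 293,775 diagnoses a year, a group with 5% annual incidence could hold at most 293,775 / 0.05 = 5,875,500 people before it used up every European case. This step uses only the protocol's own numbers.

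To turn the count into a rate I need denominators that the protocol does not give. **Assumption:** Europe has 450-750 million people, of whom 90-150 million are aged 65 or over.
- Whole population: 293,775 / 750 million = 0.039%; 293,775 / 450 million = 0.065% per year.
- Upper bound for the elderly, with every European case placed among them: 293,775 / 150 million = 0.20%; 293,775 / 90 million = 0.33% per year.

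The elderly bound is about 15 to 26 times below 5%. Section 5.2.1 admits the elderly on age alone, with no further risk criterion that would raise it.

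**3. Read 5% as prevalence of undiagnosed malignancy.** Prevalence is roughly incidence times the time for which disease is detectable but undiagnosed. Reaching 5% at the elderly bound would take 0.05 / 0.0033 to 0.05 / 0.0020, or about 15 to 26 years.

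**4. Read 5% as prevalence including MGUS and SMM.** Section 1 counts malignancies, so it says nothing against this reading. MGUS and SMM are target conditions (Section 2), and the Stage 3 work-up includes SPEP and FLC (Table 2). But the paragraph names malignancies and incidence, and it assumes a case mix that follows the incidences of the individual malignancies. Counting precursor states changes what is being counted and removes the basis for that mix.

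**5. Expected cases in the planned 900.**
- At 5%: 900 × 0.05 = 45.
- At one year of incidence, the elderly give 400 × 0.00196 to 0.00326 = 0.78 to 1.31.
- Relatives, at the population average, give 500 × 0.00039 to 0.00065 = 0.20 to 0.33.
- The total is 0.98 to 1.63, or about 1 to 2.

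One year of incidence stands in for prevalence on the assumption that disease is detectable for about a year before diagnosis. Three years would give 2.9 to 4.9. The documents give no excess risk for relatives, and Section 10.2.1 focuses recruitment on ages 55-80, so the average may be low for them. As a deliberately generous check, giving all 900 the top elderly rate yields 900 × 0.00326 = 2.9 per year of incidence.

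| Prevalence at the draw | Cases in 900 |
|---|---|
| 0.5% | 4.5 |
| 1% | 9 |
| 2% | 18 |
| 3% | 27 |
| 5% | 45 |

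**6. Precision for sensitivity (exact 95% intervals).** With 38 of 45 detected: 0.71-0.94. With 3 of 3 detected: 0.29-1.00.

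**The case against.** The best reply has four parts.

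- **Stage 3 is not sized on 5%.** A reader might infer that it is, or that the trial will run an underpowered 7,120-subject screen. The documents support neither. Enrolment is fixed at up to 900, and 7,120 is a reference figure that the protocol sets aside. It is not adopted as the size of any later study either. This part stands, so the consequence has to be stated for the 900.
- **The conflict with Section 1 is not purely internal.** The protocol prints a count without a population and never says that 5% is per year. This also stands, and the denominators above are assumptions. The break-even of 5.9 million needs no outside figure, though, and no plausible number of Europeans aged 65 or over comes near it.
- **The 5% may be a prevalence that includes MGUS.** The reference list holds two papers on MGUS prevalence (items 17 and 18), not visibly cited in the text. This reading is possible, and under it 7,120 subjects could yield about 356 positives. It cannot be called refuted. It does not rescue the paragraph, which says something else.
- **The protocol hedges.** It calls its assumptions optimistic and promises only initial estimates. That softens the claim, but it still presents the rate as a known fact and as sufficient.

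**Conclusion.** The point holds in a limited form. The five percent is uncited, has no time unit, and is the wrong kind of quantity for a single draw. As annual malignancy incidence it is about 15 to 26 times above a generous upper bound for the elderly, given an assumed 90-150 million Europeans aged 65 or over. As a prevalence that counts MGUS and SMM it may be right, but it then contradicts the stated measure, the stated diseases and the case-mix assumption. On every reading the paragraph needs correcting.

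For the 900 subjects, the claim that the rate suffices is unsupported for malignancy: 45 cases are implied, against about 1 to 2 per year of incidence under the stated assumptions. Two limits apply. The Section 1 count says nothing specific about first-degree relatives, so no multiple of risk can be derived for them. Nor does it follow that Stage 3 is uninformative: specificity, and sensitivity for precursor conditions if they are common enough, are not affected by this point.

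**What to change.** In Section 10.4:

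1. Replace the 5% incidence with the expected prevalence of undiagnosed target conditions at the single draw, with a source. State it separately for malignancy and for MGUS/SMM, and separately for the elderly and the relatives.
2. Restate the expected number of cases and the precision for the planned 900 from those prevalences.
3. Recompute 7,120, or state the case definition to which it applies.
4. Remove or qualify the statement that the rate is sufficient, and the assumption that disease types occur in the same proportions in the risk cohorts.

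Primary objective 4 can stay as written. Sensitivity for malignancy in Stage 3 would be reported descriptively with exact intervals.

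The cost is a rewritten paragraph, a sourced set of prevalences and a few recalculations, with no added subjects or procedures. The downside is that the stated Stage 3 yield becomes less favourable.
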